6.3 Patient Reported Outcomes for FACT-L

To ensure completion of the FACT-L questionnaires at the appropriate time-points, assigned research staff must adhere to the instructions in this section. The patient should complete the FACT-L questionnaires in clinic at the following times: at baseline, prior to the start of each cycle, and at the end of therapy.

Research staff should instruct the patient how to properly fill in the FACT-L questionnaire per the following instructions:

HCC #:16-054

Version Date: 008/11/2020

- All questionnaires must be completed prior to any other study procedures (baseline following informed consent) and before discussion of current disease status to avoid biasing the patient's responses to the questions.
- Provide a private environment for the patient to answer the questions.
- Provide sufficient time for the patient to complete the questionnaire at their own pace.
- Avoid assistance from relatives, friends or clinic staff to help the patient answer the questionnaires. However, if the patient is unable to read the questionnaire (due to vision impairment such as blindness or uncorrected vision, illiteracy), the questionnaires may be read out loud by trained clinic staff and responses recorded.
- When the patient completes the questionnaire, it should be handed back to the person responsible for the questionnaires, checking for completeness prior to initiating any other procedures.
- Only one answer should be recorded for each question.

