6.4 Duration of Therapy

Treatment may continue for up to 12 months (maximum 12 doses) or until one of the criteria for durvalumab discontinuation is met.

Permanent discontinuation of durvalumab

An individual subject will not receive any further investigational product if any of the following occur in the subject in question:

- Confirmation of PD and investigator determination that the subject is no longer benefiting from treatment with durvalumab
- Withdrawal of consent or lost to follow-up
- Adverse event that, in the opinion of the investigator or the sponsor, contraindicates further dosing
- Subject is determined to have met one or more of the exclusion criteria for study participation at study entry and continuing investigational therapy might constitute a safety risk
- Pregnancy or intent to become pregnant
- Any AE that meets criteria for discontinuation as defined in Appendix D.
- Grade \geq 3 infusion reaction
- Subject noncompliance that, in the opinion of the investigator or sponsor, warrants withdrawal; eg, refusal to adhere to scheduled visits

HCC #:16-054

Version Date: 008/11/2020

- Initiation of alternative anticancer therapy including another investigational agent

Subjects who are permanently discontinued from further receipt of investigational product, regardless of the reason (withdrawal of consent, due to an AE, other), will be identified as having permanently discontinued treatment.

Subjects who are permanently discontinued from receiving investigational product will be followed for safety per Appendix E or F, unless consent is withdrawn or the subject is lost to follow-up or enrolled in another clinical study. All subjects will be followed for survival. Subjects who decline to return to the site for evaluations will be offered follow-up by phone at months 2, 3, 4, 6, 8, 10, 12 after stopping treatment, and then every 2 months after that as an alternative.

Withdrawal of consent

If consent is withdrawn, the subject will not receive any further investigational product or further study observation.

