- PFS will be evaluated using the same methodology as for OS. PFS and OS will be evaluated in the unselected populations and based on PD-L1 status. The ORR and OS12 will be estimated with a 90% Wilson Score confidence interval, for the unselected population and based on PD-L1 status. HRQL at baseline, the end of each cycle, and at the end of therapy will be assessed using the FACT-L questionnaire ([name]., 2007). Total scores and subscales will be summarized for each patient, and analyzed using standard linear mixed models methods and generalized estimating equations. The primary analysis will summarize baseline QOL, average changes over the first two cycles of treatment, and average QOL in survivors at approximately 6 months and 12 months.

REFERENCES

7. EuroQol G: EuroQol--a new facility for the measurement of health-related quality of life. *Health policy (Amsterdam, Netherlands)* 1990, 16:199-208.

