APPENDIX E								
Schedule of study procedures: follow-up for subjects who have completed durvalumab treatment and achieved disease control (until confirmed progression of disease) and subjects who have discontinued durvalumab due to toxicity in the absence of confirmed progression of disease								
Evaluation	Time Since Last Dose of durvalumab							
	Day (± 3)	Months (± 1 week)						12 Months, then Every 6 Months thereafter (± 2 weeks)
	30	2	3	4	6	8	10	
Physical examination ^a	X							
Vital signs (temperature, respiratory rate, blood pressure, pulse)	Per institutional standard of care or as clinically indicated							
Weight	X							
Serum β hCG	X							
AE/SAE assessment	X	X	X					
Concomitant medications	X	X	X					
Palliative radiotherapy	As clinically indicated \longrightarrow							
ECOG performance status	X	X	X		X (and month 9)			X
Subsequent anti-cancer therapy	X	X	X	X	X	X	X	X
Survival status: phone contact with subjects who refuse to return for evaluations and agree to be contacted		X	X	X	X	X	X	X (every 2 months)
Hematology	X	X	X					X
Serum chemistry	X	X	X					
Thyroid function tests (TSH, and fT3 and fT4) ^b	X							
FACT-L questionnaire	X			X	
For subjects who achieve disease control following 12 months of treatment, patient questionnaires should be completed every 12 weeks relative to the date of enrollment until confirmed PD by RECIST 1.1 by investigational site review.
 
For subjects who discontinue study drug due to toxicity or a reason other than confirmed PD, patient questionnaires should be completed relative to the date of enrollment as follows: every 8 weeks for the first 12 months, then every 12 weeks until confirmed PD by RECIST 1.1 by investigational site review.
			

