APPENDIX F								
Schedule of study procedures: follow-up for subjects who have discontinued durvalumab treatment due to confirmed progression of disease at the discretion of the investigator								
Evaluation	Time Since Last Dose of durvalumab							
	Day (±3)	Months (±1 week)						12 Months, then Every 6 Months thereafter (±2 weeks)
	30	2	3	4	6	8	10	
Physical examination ^a	X							
Vital signs (temperature, respiratory rate, blood pressure, pulse)	Per institutional standard of care or as clinically indicated.							
Weight	X							
AE/SAE assessment	X	X	X					
Concomitant medications	X	X	X					
Palliative radiotherapy	As clinically indicated 							
ECOG performance status ^b	X	X	X					
Subsequent anti-cancer therapy	X	X	X	X	X	X	X	X
Survival status: phone contact with subjects who refuse to return for evaluations and agree to be contacted		X	X	X	X	X	X	X (every 2 months)
Serum βhCG	X							
Hematology	X	X	X					
Serum chemistry	X	X	X					
Thyroid function tests (TSH, and FT3 and FT4) ^c	X							
FACT-L questionnaire	X		X					
Tumor assessment (CT or MRI)	
For subjects who continue on durvalumab post-confirmed progression at the investigator’s discretion (following consultation with the sponsor), tumor assessments should be performed relative to the date of first infusion per Schedule of Assessments until durvalumab is stopped.
 
For subjects who discontinue durvalumab following confirmed progression, scans should be conducted according to local clinical practice until a new treatment is started (these scans are optional).
							

a. Full physical exam

b. PS to be collected if available at the 2 monthly calls to obtain subsequent anti-cancer therapy and survival status

c. Free T3 and free T4 will only be measured if TSH is abnormal. They should also be measured if there is clinical suspicion of an adverse event related to the endocrine system.

UPCI #:16-054

Version Date: 08/15-2018

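### The FACT-L schedule does not support an average over all survivors at 6 and 12 months; the reported mean will over-represent non-progressed patients, chiefly at 12 months

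*Combined protocol and SAP*

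**What the plan says.** Section 14.3, like the synopsis, makes three things the main HRQL analysis: baseline, change over the first two cycles, and "average QOL in survivors at approximately 6 months and 12 months". It names linear mixed models and generalized estimating equations. It gives no visit window, denominator or missing-data assumption for the 6- and 12-month means.

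Collection is set out in three places:

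- Section 6.3, on treatment: "at baseline, prior to the start of each cycle, and at the end of therapy".
- Appendix E, for patients off treatment without confirmed progression. Those with disease control after 12 months: "patient questionnaires should be completed every 12 weeks relative to the date of enrollment until confirmed PD by RECIST 1.1". Those who stopped for toxicity or another reason: "every 8 weeks for the first 12 months, then every 12 weeks until confirmed PD by RECIST 1.1 by investigational site review".
- Appendix F, "follow-up for subjects who have discontinued durvalumab treatment due to confirmed progression of disease": the "FACT-L questionnaire" row is marked at day 30 and month 3 after the last dose and at no later time.

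Section 6.4 has survival tracked in every patient, including those off treatment.

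**The concern.** The analysis names one population and the schedule measures another. A survivor who stopped for confirmed progression more than about three months before the time point has no scheduled form. Neither does a patient under Appendix E once progression is confirmed. Both still count as alive. Whether a form exists therefore depends on progression, which is plausibly related to the outcome being averaged.

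HRQL is a listed secondary objective, and the trial's rationale is an effective and tolerable option for PS2 patients. A 12-month figure labelled as the survivors' average, but resting on a progression-selected part of them, could be read as better quality of life than survivors as a group had.

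**Working it through.** **The plan's own figures.** The documents state no number for the HRQL summary. N = 50 and median OS 9 months come from Section 14.1. As a check on that base, exponential survival with median 9 months gives S(5) = 0.5^(5/9) = 0.68. Simulating the log-transformed Greenwood interval gives power of 85.5% (90% CI) and 77.6% (95% CI), against 85% and 78% stated. Both reproduce.

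**Survivors expected.** 50 × 0.5^(6/9) = 31.5 at 6 months; 50 × 0.5^(12/9) = 19.8 at 12 months.

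**Forms expected.** A simulation took patients from treatment to progression to death, with survival after progression set so that median OS is 9 months. Patients who stopped for progression had forms at the stop visit and 1 and 3 months after the last dose. Assumptions not in the documents: median PFS 2 to 6 months, 20% of PFS events are deaths, a window of ±1 month, no toxicity stops, no missed forms. Treatment stopped either at progression or 2 months later. The second case is about the 8-week scan interval, since the Section 11 footnote prefers confirmation of progression at the next scheduled scan.

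| Median PFS (months) | Time (months) | Progressed, all survivors | Survivors with form: stop at PD | Progressed, those with form | Survivors with form: stop 2 months later | Progressed, those with form |
|---|---|---|---|---|---|---|
| 2 | 6 | 80% | 47% | 59% | 81% | 76% |
| 2 | 12 | 96% | 11% | 64% | 19% | 79% |
| 3 | 6 | 62% | 65% | 42% | 89% | 57% |
| 3 | 12 | 83% | 31% | 46% | 42% | 60% |
| 4 | 6 | 47% | 77% | 31% | 93% | 43% |
| 4 | 12 | 66% | 53% | 35% | 63% | 45% |
| 6 | 6 | 25% | 91% | 18% | 97% | 23% |
| 6 | 12 | 32% | 85% | 20% | 91% | 25% |

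**Hand check, PFS 3 months, stop at progression.** Progression-free patients number 50 × 0.5^(6/3) = 12.5 and 50 × 0.5^(12/3) = 3.1. The simulation has 32.8 and 18.6 alive, with forms for 21.5 and 5.8. Progressed share of survivors: 1 − 12.5/32.8 = 62%; 1 − 3.1/18.6 = 83%. Progressed share of those with a form: 1 − 12.5/21.5 = 42%; 1 − 3.1/5.8 = 46% (rounded). These agree with the table.

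**Effect on the mean.** If progressed patients score D points lower on average, overstatement = D × (progressed share of survivors − progressed share of those with a form). With D assumed to be 5 to 15 points, at PFS 3 months:

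- Stop at progression, 6 months: (0.62 − 0.42) × D = 0.20 × D, or 1.0 to 3.0 points.
- Stop at progression, 12 months: (0.83 − 0.46) × D = 0.37 × D, or 1.9 to 5.6 points.
- Stop 2 months later: (0.62 − 0.57) × D = 0.3 to 0.8 points at 6 months; (0.83 − 0.60) × D = 1.2 to 3.5 points at 12 months.

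**Sensitivity.** At PFS 3 months with stop at progression, a ±0.5-month window lowers the proportion with a form to 58% and 22%; ±1.5 months gives 76% and 31%. The gap also depends on survival after progression: with median OS only 5 months and PFS 3 months, forms exist for 86% and 80% of survivors.

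**The case against.** Three stronger readings are tempting, and the documents support none of them.

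- *A reader might infer that progressed patients are never measured.* They are, for a time: at end of therapy and twice after the last dose under Appendix F. Progression alone does not end treatment either. Section 6.4 requires "Confirmation of PD and investigator determination that the subject is no longer benefiting from treatment with durvalumab", and Appendix F provides for "subjects who continue on durvalumab post-confirmed progression", who would stay on the per-cycle forms.
- *A reader might infer that the mean cannot be estimated.* An observed-case mean can be computed, and a mixed model can give a survivor mean under missing-at-random, with some post-progression data to draw on. The weakness is that this assumption is unstated and doubtful. Unweighted GEE needs a stronger assumption still.
- *A reader might infer that the figure will describe mainly non-progressed patients.* That depends on PFS and on treatment beyond progression. At PFS 2 months, most patients with a form have progressed (59% and 64%).

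The point's importance is also limited. The objective concerns quality of life associated with durvalumab therapy, and the first two summaries are hardly affected. HRQL carries no threshold or test, and the rule for calling durvalumab promising rests on OS, read alongside safety and durable responses. Tolerability has its own primary endpoint.

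All of this stands and narrows the point. It does not make the label accurate: in every scenario tabulated, progressed patients are a smaller share of those with forms than of survivors.

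**Conclusion.** The point holds as a mismatch between the named population and the schedule. It matters chiefly at 12 months; at 6 months most survivors have a form in nearly all scenarios. At PFS 3 months with treatment stopped at progression, about 6 forms would stand for about 19 survivors at 12 months.

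The mechanism follows from the documents, but the size does not. PFS, time on treatment after progression and the deficit D are all assumed. The upward direction requires worse quality of life after progression, which is plausible but not quantified in the documents. The calculation also gives progressed patients with and without a form the same average score; if quality of life keeps falling with time since progression, the overstatement would be larger. Sample size, power and the primary analyses are unaffected. The wording should be corrected, but no trial decision turns on it.

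**What to change.** In Section 14.3 and the synopsis, relabel the summary as mean QOL among survivors with a scheduled FACT-L in a stated window around 6 and 12 months. Define that group as patients on therapy, patients off therapy without confirmed progression, and patients within about 3 months of the last dose after progression. The third group must be named, or the new label would leave out patients who do contribute forms. Report forms received over patients alive at each time, show the means by progression status, and do not describe the result as the average for all survivors. If a model-based survivor mean is also given, state its missing-data assumption. This costs a few lines of text and no new data.

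Optional, to keep all survivors as the target: add FACT-L near 6 and 12 months from first dose, at existing follow-up contacts, for patients off treatment after progression. That means up to two extra forms per patient. If completed by telephone, it also changes the in-clinic mode set in Section 6.3, which would need amending.

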APPENDIX A PERFORMANCE STATUS CRITERIA

ECOG Performance Status Scale		Karnofsky Performance Scale	
Grade	Descriptions	Percent	Description
0	Normal activity. Fully active, able to carry on all pre-disease performance without restriction.	100	Normal, no complaints, no evidence of disease.
		90	Able to carry on normal activity; minor signs or symptoms of disease.
1	Symptoms, but ambulatory. Restricted in physically strenuous activity, but ambulatory and able to carry out work of a light or sedentary nature (e.g. , light housework, office work).	80	Normal activity with effort; some signs or symptoms of disease.
		70	Cares for self, unable to carry on normal activity or to do active work.
2	In bed <50% of the time. Ambulatory and capable of all self-care, but unable to carry out any work activities. Up and about more than 50% of waking hours.	60	Requires occasional assistance, but is able to care for most of his/her needs.
		50	Requires considerable assistance and frequent medical care.
3	In bed >50% of the time. Capable of only limited self-care, confined to bed or chair more than 50% of waking hours.	40	Disabled, requires special care and assistance.
		30	Severely disabled, hospitalization indicated. Death not imminent.
4	100% bedridden. Completely disabled. Cannot carry on any self-care. Totally confined to bed or chair.	20	Very sick, hospitalization indicated. Death not imminent.
		10	Moribund, fatal processes progressing rapidly.
5	Dead.	0	Dead.

HCC #:16-054

Version Date: 008/11/2020

APPENDIX B: FACT-L (VERSION 4)

Assessment Date: ___/___/___
mm/dd/yyyy

FACT-L (v4) Worksheet

Protocol: 16-054

Patient Initials: ___

Patient number: ___

Below is a list of statements that other people with your illness have said are important. **Please circle or mark one number per line to indicate your response as it applies to the past 7 days.**

PHYSICAL WELL-BEING		Not at all	A little bit	Some-what	Quite a bit	Very much
GP1	I have a lack of energy	0	1	2	3	4
GP2	I have nausea	0	1	2	3	4
GP3	Because of my physical condition, I have trouble meeting the needs of my family	0	1	2	3	4
GP4	I have pain	0	1	2	3	4
GP5	I am bothered by side effects of treatment	0	1	2	3	4
GP6	I feel ill	0	1	2	3	4
GP7	I am forced to spend time in bed	0	1	2	3	4

SOCIAL/FAMILY WELL-BEING		Not at all	A little bit	Some-what	Quite a bit	Very much
GS1	I feel close to my friends	0	1	2	3	4
GS2	I get emotional support from my family	0	1	2	3	4
GS3	I get support from my friends.....	0	1	2	3	4
GS4	My family has accepted my illness	0	1	2	3	4
GS5	I am satisfied with family communication about my illness.....	0	1	2	3	4
GS6	I feel close to my partner (or the person who is my main support)	0	1	2	3	4
Q1	Regardless of your current level of sexual activity, please answer the following question. If you prefer not to answer it, please mark this box  and go to the next section.					
GS7	I am satisfied with my sex life	0	1	2	3	4

Assessment Date: ___/___/___
mm/dd/yyyy

FACT-L (v4) Worksheet

Protocol: 16-054

Patient Initials: ___

Patient number: ___

Please circle or mark one number per line to indicate your response as it applies to the past 7 days.

EMOTIONAL WELL-BEING

		Not at all	A little bit	Some- what	Quite a bit	Very much
GE1	I feel sad	0	1	2	3	4
GE2	I am satisfied with how I am coping with my illness	0	1	2	3	4
GE3	I am losing hope in the fight against my illness	0	1	2	3	4
GE4	I feel nervous	0	1	2	3	4
GE5	I worry about dying	0	1	2	3	4
GE6	I worry that my condition will get worse	0	1	2	3	4

FUNCTIONAL WELL-BEING

		Not at all	A little bit	Some- what	Quite a bit	Very much
GF1	I am able to work (include work at home)	0	1	2	3	4
GF2	My work (include work at home) is fulfilling	0	1	2	3	4
GF3	I am able to enjoy life	0	1	2	3	4
GF4	I have accepted my illness	0	1	2	3	4
GF5	I am sleeping well	0	1	2	3	4
GF6	I am enjoying the things I usually do for fun	0	1	2	3	4
GF7	I am content with the quality of my life right now	0	1	2	3	4

Assessment Date: ___/___/___
 mm/dd/yyyy

FACT-L (v4) Worksheet

Protocol: 16-054

Patient Initials: ___

Patient number: ___

Please circle or mark one number per line to indicate your response as it applies to the past 7 days.

ADDITIONAL CONCERNS		Not at all	A little bit	Some- what	Quite a bit	Very much
B1	I have been short of breath	0	1	2	3	4
C2	I am losing weight	0	1	2	3	4
L1	My thinking is clear	0	1	2	3	4
L2	I have been coughing	0	1	2	3	4
B5	I am bothered by hair loss	0	1	2	3	4
C6	I have a good appetite	0	1	2	3	4
L3	I feel tightness in my chest	0	1	2	3	4
L4	Breathing is easy for me	0	1	2	3	4
Q3	Have you ever smoked? No ___ Yes ___ If yes:					
L5	I regret my smoking	0	1	2	3	4

APPENDIX C: DURVALUMAB DOSE CALCULATIONS

Durvalumab Dosing

The durvalumab dosing should be done depending on subject weight (if subject is < 30kg):

1. Cohort dose: X mg/kg
2. Subject weight: Y kg
3. Dose for subject: XY mg = X (mg/kg) × Y (kg)
4. Dose to be added into infusion bag:

$$\text{Dose (mL)} = \text{XY mg} / 50 \text{ (mg/mL)}$$

where 50 mg/mL is durvalumab nominal concentration

The corresponding volume of durvalumab should be rounded to the nearest tenth mL (0.1 mL).

Dose adjustments for each cycle only needed for greater than 10% change in weight.

5. The theoretical number of vials required for dose preparation is the next greatest whole number of vials from the following formula:

$$\text{Number of vials} = \text{Dose (mL)} / 10 \text{ (mL/vial)}$$

Example:

1. Cohort dose: 10 mg/kg
2. Subject weight: 30 kg
3. Dose for subject: 300 mg = 10 (mg/kg) × 30 (kg)
4. Dose to be added into infusion bag:

$$\text{Dose (mL)} = 300 \text{ mg} / 50 \text{ (mg/mL)} = 6.0 \text{ mL}$$

5. The theoretical number of vials required for dose preparation:

$$\text{Number of vials} = 6.0 \text{ (mL)} / 10.0 \text{ (mL/vial)} = 1 \text{ vials}$$

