6. TREATMENT PLAN

6.1 Durvalumab Administration

Treatment will be administered on an outpatient basis. No investigational or commercial agents or therapies other than those described below may be administered with the intent to treat the patient's malignancy.

Regimen Description					
Agent	Premedications / Precautions	Dose	Route	Schedule	Cycle Length
Durvalumab	N/A	** in 500 cc NS	IV over 60 minutes (± 5 minutes)	Day 1	28 days (4 weeks)

** Dose calculation is based in patient weight at the time of each treatment. See section 6.1.1 for fixed dose information for subjects weighing greater than or equal to 30 kg and Appendix C for calculation of dose for subjects with weight of less than 30 kg.

Study drug preparation

For patients weighing ≥ 30 kg, a fixed dose of 1500 mg Q4W durvalumab (equivalent to 20 mg/kg Q4W) (based on an average body WT of 75 kg) should be prepared. For subjects <30 kg body weight, dose is determined using body mass, calculating the stock volume of durvalumab to achieve the accurate dose according to Appendix C.

Preparation of durvalumab doses for administration with an IV bag

The dose of durvalumab for administration must be prepared by the Investigator's or site's designated IP manager using aseptic technique. Total time from needle puncture of the durvalumab vial to the start of administration should not exceed:

- 24 hours at 2°C to 8°C (36°F to 46°F)
- 4 hours at room temperature

If in-use storage time exceeds these limits, a new dose must be prepared from new vials. Infusion solutions must be allowed to equilibrate to room temperature prior to commencement of administration.

No incompatibilities between durvalumab and polyvinylchloride or polyolefin IV bags have been observed. Dose of 1500mg durvalumab for patients >30 kg will be administered using an IV bag containing 0.9% (w/v) saline or 5% (w/v) dextrose for IV infusion with a final durvalumab concentration ranging from 1 to 20 mg/mL, and delivered through an IV administration set with a 0.2- or 0.22- μm in-line filter.

Remove a volume of IV solution from the IV bag equal to the calculated volume of durvalumab to be added to the IV bag prior to addition of durvalumab. Next, the volume of durvalumab (i.e., 30.0 mL for 1500 mg of durvalumab) is added to the IV bag such that final concentration is within 1 to 20 mg/mL (IV bag volumes 100 to 1000 mL). Mix the bag by gently inverting to ensure homogeneity of the dose in the bag.

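### Appendix C never sets the mg/kg dose for low-weight patients, and section 6.1 gives the 1500 mg fixed dose at exactly 30 kg, which section 2.2.2 advises against

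*Combined protocol and SAP*

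**What the plan says.** **The route.** Section 2.2.2 (Fixed Dosing) recommends the fixed dose only above 30 kg, gives endotoxin exposure as the reason, and sends patients at 30 kg or below to Appendix C. Section 6.1 also refers low-weight patients to Appendix C.

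**The weight-based dose.** Appendix C defines the dose as X times body weight, with "Cohort dose: X mg/kg" as its first line. Its worked example then uses "Cohort dose: 10 mg/kg" for a 30 kg patient.

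**The study dose.** Under Study drug preparation, section 6.1 says that "a fixed dose of 1500 mg Q4W durvalumab (equivalent to 20 mg/kg Q4W) (based on an average body WT of 75 kg) should be prepared". Section 2.2.2 states the same equivalence.

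**The boundary.**
- Section 2.2.2: fixed above 30 kg, weight-based at 30 kg or below.
- Section 6.1, regimen table footnote: "See section 6.1.1 for fixed dose information for subjects weighing greater than or equal to 30 kg". Study drug preparation uses the same cut-off (30 kg and above).
- Section 6.1, IV bag paragraph: "Dose of 1500mg durvalumab for patients >30 kg will be administered using an IV bag".
- Section 6.1, later paragraphs: the low-weight group is 30 kg or below in one sentence and below 30 kg in another.
- Appendix C: "The durvalumab dosing should be done depending on subject weight (if subject is < 30kg", although its example patient weighs 30 kg.

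**The reference weight.** The regimen table footnote says "Dose calculation is based in patient weight at the time of each treatment". Later text in section 6.1 makes baseline weight the default unless it changes by 10% or more, and allows dosing-day weight where that is the institutional standard. Appendix C says "Dose adjustments for each cycle only needed for greater than 10% change in weight".

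**The concern.** A weight-based rule needs two inputs. The patient supplies the weight, and the protocol has to supply the mg/kg level, which it does not. The word cohort in Appendix C refers to nothing here, because the trial has one arm and one regimen. Whoever prepares the dose must choose X, and the nearest number is the example's 10 mg/kg. Wherever the background sections give a schedule with a 10 mg/kg regimen, it is every two weeks (Q2W), while this trial doses every four weeks. Carrying the example over would halve the dose. The protocol would also offer no stated weight-based dose against which to judge a dosing deviation.

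The boundary matters for a different reason. At exactly 30 kg, two places in section 6.1 call for a dose that the protocol's own safety rationale in section 2.2.2 advises against.

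**Working it through.** **Inputs.** Fixed dose 1500 mg Q4W and reference weight 75 kg (sections 2.2.2 and 6.1). Earlier fixed dose 750 mg Q2W, chosen to approximate 10 mg/kg (section 2.2.2). Stock concentration 50 mg/mL and 10 mL per vial (Appendix C). Bag of 500 cc (regimen table). Final concentration 1 to 20 mg/mL and bags of 100 to 1000 mL (section 6.1, stated there for the 1500 mg dose).

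**1. Reproduce the Appendix C example.** Dose = X × weight; volume = dose / 50; vials = volume / 10, rounded up.
- 10 × 30 = 300 mg; 300 / 50 = 6.0 mL; 6.0 / 10 = 0.6, so 1 vial. This agrees with the appendix.

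**2. Compare with the study dose.**
- 1500 / 75 = 20 mg/kg Q4W, as the protocol states.
- 750 / 75 = 10 mg/kg Q2W, so the example's figure matches the two-weekly regimen.
- Example against the study's equivalent: 10 / 20 = 0.5.

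**3. Rework the example at 20 mg/kg.**
- 20 × 30 = 600 mg; 600 / 50 = 12.0 mL; 12.0 / 10 = 1.2, so 2 vials.

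**4. Check the concentration.** Section 6.1 removes the same volume of fluid as it adds, so the bag volume is the final volume. In the 500 mL bag:

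| Weight | Dose at 20 mg/kg | Concentration |
|---|---|---|
| 30 kg | 600 mg | 600 / 500 = 1.2 mg/mL |
| 25 kg | 500 mg | 500 / 500 = 1.0 mg/mL |
| 24 kg | 480 mg | 480 / 500 = 0.96 mg/mL |

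Below 25 kg a bag smaller than 500 mL is needed to stay at 1 mg/mL or more. The present example gives 300 / 500 = 0.6 mg/mL, also below that floor. Because the range is stated for the 1500 mg dose, this is only suggestive about the intended X.

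**5. The boundary at 30.0 kg.**
- Fixed dose: 1500 mg, or 1500 / 30 = 50 mg/kg.
- Weight-based at 20 mg/kg: 600 mg, so the fixed dose is 1500 / 600 = 2.5 times as large.
- Weight-based with the example's figure: 300 mg, so 1500 / 300 = 5 times as large.
- Just above the boundary: 1500 / 30.1 = 49.8 mg/kg under either wording. The step in dose comes from the 30 kg cut-off itself and remains after the signs are aligned.

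**The case against.** The best reply is that the answer can be inferred and hardly anyone needs it. The only per-kg equivalent stated for this trial's four-weekly regimen is 20 mg/kg, and the 10 mg/kg figure sits under a label marking it as an example of volume and vial arithmetic. Section 2.2.2 also refers investigators to the Investigator's Brochure, which may cover low weights; that cannot be checked here. Enrolment is 50 adults, and the protocol's own fixed-dose simulation used weights of 40 to 120 kg, so the weight-based route begins 10 kg below that range.

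Most of this stands, and it sets the size of the point. It does not supply the missing value: the protocol chose to write this route, sections 3.1 and 3.2 set no minimum weight, and an inference is not a dosing instruction.

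Some stronger readings are tempting, but the documents do not support them:
- *That the protocol prescribes 10 mg/kg.* It does not; the figure appears only in an example.
- *That 20 mg/kg is already the specified dose.* It is stated only as the equivalent of 1500 mg at 75 kg, which is why the supplier should confirm it.
- *That the reference-weight rules contradict each other in a way that changes doses.* Section 6.1 expressly permits both baseline and dosing-day weight. Appendix C says when adjustment is needed and does not forbid adjusting at exactly 10%. What remains is untidy wording.
- *That the 30 kg wording causes a calculable harm.* The documents give no endotoxin content or limit.
- *That the pointer to section 6.1.1 shows missing dosing content.* No such heading appears in section 6.1, but the fixed-dose information is there under Study drug preparation. The slip is clerical.

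**Conclusion.** The point holds, at minor severity. Appendix C is the only dosing rule for patients sent to weight-based dosing, and it leaves the mg/kg dose unset. Its sole figure is half the study's stated Q4W equivalent, so copying it would mean 300 mg in place of 600 mg at 30 kg. Separately, the 30-kg-and-above wording in section 6.1 conflicts with the endotoxin-based limit in section 2.2.2, and the conflict changes the route only for a recorded weight of 30.0 kg.

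Two assumptions are involved. The first is that 20 mg/kg Q4W is the intended X, which is inferred from the fixed-dose equivalence. The second is that few or no enrolled patients will weigh 30 kg or less; the documents give no weight data for this population, and the simulated 40 to 120 kg range is the nearest evidence. A reader might infer a threat to the trial's conclusions, but no endpoint, sample size or analysis depends on this text.

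**What to change.** 1. In Appendix C, replace X with a stated dose, proposed as 20 mg/kg Q4W subject to the drug supplier's confirmation.
2. Rework the example: 30 kg, 600 mg, 12.0 mL, 2 vials. Add that the bag volume must keep the concentration within 1 to 20 mg/mL, which means a bag under 500 mL for patients below 25 kg.
3. Use one boundary throughout section 6.1 and Appendix C, matching section 2.2.2: above 30 kg fixed dose, 30 kg or less weight-based.
4. As tidying only, align the regimen table footnote and the 10% wording in Appendix C with the reference-weight text in section 6.1, and point the footnote to Study drug preparation instead of section 6.1.1.

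The cost is a text correction to section 6.1 and Appendix C and one confirmation from the supplier. Design, sample size and analysis stay as they are.
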